APPENDIX 7 NUMERICAL RATING SCALE

Investigational Device: ThermoRF

Protocol No.: Thermo_0005

Version Date: Final 10-May-2016

APPENDIX 8 APPLICATION OF NON-SIGNIFICANT RISK

THERMIAGEN, LLC LETTER OF APPLICATION FOR NONSIGNIFICANT RISK DETERMINATION FOR THE THERMIRF® DEVICE (V0.1 12.07.14)

Description of Investigational Product:

[figure not shown]
Name of the device: ThermoRF

Description of the device: The ThermoGen, LLC ThermoRF is a non-invasive, transcutaneous radiofrequency device that is FDA cleared for dermatological and general surgical procedures for electrocoagulation and hemostasis (K130689).

The ThermoRF has been tested by a third party (Intertek Testing Services NA Inc.) for conformance to IEC 60601-1-2 (EMC) and IEC 60601-1 (electrical safety). Third party verification of IEC 60601-1-4 and IEC 60601-1-6 Collateral Standards was performed as well.

The ThermoRF is a 20 watt electrothermal RF generator that continuously monitors temperature and impedance. It provides controlled temperature tissue heating as its mechanism of action.

Name: ThermoRF

Control/Connections	Function
1. RF ON (blue light)	Illuminated when generator is delivering RF power
2. STIM ON (yellow light)	Illuminated when generator is delivering Stimulate Power
3. FAULT (red light)	Illuminated when a fault condition is detected
4. Neutral electrode connection port	Used to connect a neutral electrode (grounding pad) to the generator
5. Device connection port	Used to connect RF electrode accessories to generator
6. Display window	Displays generator information, modes, and operating parameters.
7. Soft Keys	STIM: Motor; ThermoTight, ThermoSmooth, ThermoRase, Help/Exit, Start, Reset, and OK
8. RF ON Button	Start or stops RF power delivery
9. Up/down buttons	Used to increase or decrease function settings
10. Stim output knob	Adjusts the stimulate output voltage. Push and release the knob to turn Stimulate power on/off.

Investigational Device: ThermoRF

Protocol No.: Thermo_0005

Version Date: Final 10-May-2016

[figure not shown]

Figure 2. ThermoAesthetics™ ThermoRF™ System rear panel.

Control/Connections	Function
1. On/Off rocker switch	Turn the generator main power on/of
2. Fuse access door	Access for fuse replacement
3. Power cord connector	Input module
4. RS-232 connector	For service use only
5. Equipotential compensator terminal (case ground)	Bring equipment into the same case potential as the generator
6. Footswitch connector	Connect pneumatic footswitch to the generator
7. Security door	Access for software upgrades (Authorized user only)

ThermoRF is a main powered device; the specifications of which are:

Height: 5.75"

Width: 12.5"

Depth: 13.0"

Weight: 12.6 lbs.

SPECIFICATIONS

Parameters	ThermoRF
Dimensions ThermoRF Generator	W:12.5 * D:13.0 * H:5.75
Internal Display	LCD Display
ThermoRF Generator Specifications	
Input Power	100-120/200-240 + 10%, 50/60 Hz
Output Power	20 watts (maximum) into 50-300Ω
Output Voltage in Stimulate Mode	0-10 V
Output Voltage in RF Lesion Mode	0-20 V
Operating Frequency	460 kHz (+5 kHz)
Power Delivery Modes	Stimulate Mode, ThermoTight Mode, ThermoRase Mode, ThermoSmooth Mode Pulsed RF Mode, Biomed (calibration-test) Mode
Set Temperature Range	35-90oC, this range varies for each Power Delivery Mode

Investigational Device: ThermoRF

Protocol No.: Thermo_0005

Version Date: Final 10-May-2016

Waveform	Sine wave for RF Lesion and Pulsed RF Modes, Square wave for Stimulate Modes
Protection (per IEC 60601-1)	Class I, Type BF Applied Part-defibrillator proof, IXP0, Continuous Operation. Not suitable for use in the presence of a flammable anesthetic mixture.
Controls	Line Power On/OFF, RF On/OFF, Stimulate Output, Front Panel Soft Keys (Start, Set Temp, Set Profile, Reset, Width, Frequency, and Mode Selection)
Displays	Impedance, Actual Temp, Elapsed Time, Paused, Volts, Frequency
Electrode surface	180 mm ²
Subject contacting part	Yes
Subject contacting materials	Surgical Stainless Steel

Device Preparation and Administration of Study Intervention/Investigational Product:

The device will administer up to 20 Watts of radiofrequency energy.

DETERMINATION OF DEVICE SAFETY

RISK AND PREVENTION

The ThermoRF® Device is classified by the FDA/IEC as a Class 2 radiofrequency device. The device has risk of burns or fire, and therefore, cannot be used near conductive materials such as metal bed parts, inner-spring mattress, etc. A disposable grounding pad is used to ground the electrical current. Furthermore, the subject will not be placed into contact with metal parts which are grounded or which have appreciable capacitance to earth. The device cannot be used in subjects with a pacemaker, implantable defibrillators, or monitoring equipment.

FDA DETERMINATION OF NON-SIGNIFICANT RISK (NSR) STATUS

The ThermoGen LLC ThermoRF is a radiofrequency device that is FDA cleared for dermatological and general surgical procedures for electrocoagulation and hemostasis (K130689).

N.B.; The ThermoRF is technically identical to the Symphony RF, the marketing name of the device was changed from Symphony RF to ThermoRF. No technical modifications were made. (K130689).

1. 510(k) # 130689

Device Name: SymphonyRF Generator (ThermoRF)

Indication for use: dermatological and general surgical procedures for electrocoagulation and hemostasis; and to create lesions in nervous tissue

2. 510(k) #: K-033981

Device Name: Smith and Nephew ElectroThermal 20S Spine Generator

Indication of use: Intended to create lesions in nervous tissue, and to coagulate and decompress disc material when used in combination with Smith and Nephew thermal/coagulating probes.

3. 510(k) #: K121858

Device Name: The Acessa System

Investigational Device: ThermoRF

Protocol No.: Thermo_0005

Version Date: Final 10-May-2016

Indication of use: Percutaneous use for laparoscopic coagulation and ablation of soft tissue

4. 510(k) #: K121481

Device Name: The INFINI Radiofrequency System

Indication of use: For use in dermatologic and general surgical procedures for electrocoagulation and hemostasis, and the percutaneous treatment of facial wrinkles

5. 510(k) #: K082391

[figure not shown]
Device Name: Primaeva Medical

Indication for use: For use in dermatologic and general surgical procedures for electrocoagulation and hemostasis, and the percutaneous treatment of wrinkles

IRB approved study: The protocol was reviewed and approved by the local ethics committee (Independent Investigational Review Board, Inc, Plantation, FL, USA) Millheiser LS, Pauls RN, Herbst SJ, Chen BH. Radiofrequency treatment of vaginal laxity after vaginal delivery: non-surgical vaginal tightening. J Sex Med. 2010; 7(9):3088-95.

DEVICE LABELING

The ThermoRF is manufactured in accordance with the Good Manufacturing Procedures set forth by the FDA. Per CE (Certified European) standards and testing results and has been validated by a third party (Intertek Testing Services NA Inc. Report Reference No. 100584146BOX-004) for conformance to IEC 60601-1-2 (EMC) and IEC 60601-1 (electrical safety). Third party verification of IEC 60601-1-4 and IEC 60601-1-6 Collateral Standards was performed as well.

In addition, the device used in this clinical study shall be labeled with the following statement: NON-SIGNIFICANT RISK STATEMENTS

“CAUTION – Investigational device. Limited by United States law to Investigational use.”

Do you contend that this device as used in this protocol is an NSR device?

Yes No

Has another IRB decided this device is SR?

Yes No

Does this type of device appear as SR on the FDA Information Sheet?

Yes No

Investigational Device: ThermoRF

Protocol No.: Thermo_0005

Version Date: Final 10-May-2016

APPENDIX 9 THERMI_RF USER MANUAL 4002-01 REV C.PDF (1MB)

The User Manual is on-file in the sponsor Trial Master File (TMF), and a copy provided to the investigator in the Site Master File.

Investigational Device: ThermoRF

Protocol No.: Thermo_0005

Version Date: Final 10-May-2016

APPENDIX 10 BLINDED RATER VALIDATION GUIDELINES

The blinded-rater validation guidelines can be found in the sponsor Trial Master File (TMF)

## 1 ABBREVIATIONS

Abbreviation	Definition
AE	Adverse Event
BBA	Boston Biomedical Associates
CRF	Case Report Forms
CSR	Clinical Study Report
FDA	United States Food and Drug Administration
ITT	Intent-To-Treat Population
MedDRA	Medical Dictionary for Regulatory Activities
NRS	Numerical Rating Scale
P-GAIS	Physician Global Aesthetic Improvement Scale
P-GSQ	Physician Global Satisfaction Questionnaire
PPP	Per-Protocol Population
PRA	Percutaneous Radiofrequency Ablation
PT	Preferred Term
SAE	Serious Adverse Event
SAP	Statistical Analysis Plan
S-GAIS	Subject Global Aesthetic Improvement Scale
SGSQ	Subject Global Satisfaction Questionnaire
SOC	System Organ Class
SOP	Standard Operating Procedure
TEAE	Treatment Emergent AEs

## 2 SUMMARY

TITLE	An open-label, single-center, single-treatment, safety and effectiveness evaluation of percutaneous radiofrequency in achieving submental lift.
PREFACE	This Statistical Analysis Plan (SAP) describes the planned analysis and reporting for ThermiGen, LLC protocol Thermi_0005 (An open-label, single-center, single-treatment, safety and effectiveness evaluation of percutaneous radiofrequency in achieving submental lift). This study is being conducted to assess the safety and effectiveness of the ThermiRF in the treatment of submental skin laxity.
PURPOSE	
The following documents were reviewed in preparation of this SAP:
 
 
• Clinical Research Protocol Thermi_0005, issued 10MAY2016
 
• Case report forms (CRFs) issued 18AUG2016 for Protocol Thermi_0005
 
 
The purpose of this SAP is to outline the planned analyses in support of the Clinical Study Report (CSR) for protocol Thermi_0005. Exploratory analyses not necessarily identified in this SAP may be performed to support the clinical development program. Any post-hoc, or unplanned, analyses not identified in this SAP will be clearly identified in the respective CSR.

STUDY OBJECTIVES	
Primary Efficacy: The primary efficacy endpoint is the improvement in overall lift of the submental area at 90 days as determined by a quantitative assessment based on 3D photography.
 
Secondary Efficacy: The secondary endpoint is overall aesthetic improvement of the submental area and jawline definition at Days 90 and 180 evaluated by the investigator and subject using the following subjective assessments:
 
 
1. Qualitative assessment based on 2D photography performed by blinded panel
 
2. Physician – Global Aesthetic Improvement Scale Scores (P-GAIS)
 
3. Subject – Global Aesthetic Improvement Scale Scores (S-GAIS)
 
4. Physician – Global Satisfaction Questionnaire (P-GSQ)
 
5. Subject – Global Satisfaction Questionnaire (S-GSQ)
 
 
Each individual endpoint will be based on study subject population response for each individual endpoint.
 
Safety: Safety will be evaluated using the following measures:
 
 
1. Numerical Rating Scale (NRS), a 10-point pain scale
 
2. Self-reported and observed adverse events
 
 
Exploratory: Also of interest is the elasticity measurement at Days 90 and 180.
 
This study is a prospective, single-center, open-label study for the evaluation of the ThermiRF device in the treatment of submental skin laxity.
 
No annual reports for the FDA are anticipated prior to the end of data collection and database lock due to the short nature of this study.
 
A single interim analysis is planned to support a manuscript and presentation. Final study results will not be made available until post database lock.
 
All final planned analyses identified in this SAP will be completed after the last subject has completed their 6 month follow up.

STUDY DESIGN	
INTERIM ANALYSES	
FINAL ANALYSES	

### 3 SEQUENCE OF PLANNED ANALYSES

#### 3.1 INTERIM ANALYSES

##### 3.1.1 ANNUAL REPORTS

As this study is expected to be completed within one year, no annual reports are anticipated at this time.

##### 3.1.2 OTHER INTERIM REPORTS

An aggregate review of data to support a publication and/or presentation is anticipated at this time. The timing of the interim report is expected to occur prior to database lock and prior to the final analysis.

#### 3.2 FINAL ANALYSES AND REPORTING

All final, planned, analyses identified in the protocol and in this SAP will be performed only after the last subject has completed the Day 180 follow-up visit. Key statistics and study results will be made available to ThermiGen, LLC following database lock. Any post-hoc, exploratory analyses completed to support planned study analyses, which were not identified in this SAP, will be documented and reported as necessary. Any results from these unplanned analyses will also be clearly identified as post-hoc analyses.

## 4 STUDY OBJECTIVES AND ENDPOINTS

### 4.1 STUDY OBJECTIVES

#### 4.1.1 PRIMARY OBJECTIVE/ENDPOINT

The primary endpoint is an improvement of at least 20 mm^2 in overall lift of the submental area at Day 90 as determined by a quantitative assessment based on 3D photography.

#### 4.1.2 SECONDARY OBJECTIVE/ENDPOINTS

The secondary endpoint is overall aesthetic improvement of the submental area and jawline definition at Days 90 and 180 evaluated by the investigator and subject using the following subjective assessments:

1. Qualitative assessment based on 2D photography performed by blinded panel
2. Physician – Global Aesthetic Improvement Scale Scores (P-GAIS)
3. Subject – Global Aesthetic Improvement Scale Scores (S-GAIS)
4. Physician – Global Satisfaction Questionnaire (P-GSQ)
5. Subject – Global Satisfaction Questionnaire (S-GSQ)

Each individual endpoint will be based on study subject population response for each individual endpoint.

#### 4.1.3 SAFETY ENDPOINTS

The safety endpoints will be self-reported and observed adverse events along with the reporting of the Numerical Rating Scale (NRS) as a 10-point pain scale.

## 5 SAMPLE SIZE

The null and alternative hypotheses are:

$$\begin{aligned}
 H_0: \pi &\leq 0.45 \text{ (or 45\%)} \text{ vs.} \\
 H_a: \pi &> 0.45
 \end{aligned}$$

where  $\pi$  is the true proportion of subjects with at least 20 mm^2 lift. Under the assumptions that

1.  $\pi = 0.70$  (or 70%) for subjects not prematurely withdrawing from the study; and
2. The dropout rate is 12.5% and all dropouts will be considered as non-responders

a sample of size 70 enrolled subjects provides approximately 85% power to reject the null hypothesis in favor of the alternative at a one-sided  $\alpha=0.05$ .

## 6 ANALYSIS POPULATIONS

### 6.1 INTENT TO TREAT POPULATION (ITT)

The intent-to-treat (ITT) population for this study includes all subjects that signed the informed consent form, meet inclusion/exclusion criteria, and are enrolled in the study. The primary efficacy analysis will be performed using this population.

### 6.2 PER-PROTOCOL POPULATION (PP)

The per-protocol population (PP) for this study will include all subjects who have completed the Day 90 visit, have an evaluable photograph to measure the area of lift from the Day 90 visit, have not used an excluded medication, and do not have a major protocol violation (see Attachment 1).

### 6.3 SAFETY

The safety population of this study will include all enrolled subjects who received at least one treatment.

For clarification purposes of the analysis populations described in sections 6.1 – 6.3, the following table from section 8.6.2 of the clinical protocol has been included here for reference (Table 1).

**Table 1.** Subject Status Classification

Classification	Criteria
Screen Failure	Signs the ICD but does not meet entry criteria or withdraws prior to Visit 2.
Enrolled	Signs the ICD and met all inclusion/exclusion criteria
Treated	Signs the ICD and successfully completes V2
Discontinued/Withdrawal	Signed the ICD but does not successfully complete any visits
Completed	Signs the ICD and successfully completes all study visits

## 6.4 RATER AGREEMENT POPULATION

Thirty subjects, chosen in sequential order of enrollment, will have 2D photos taken at Day 60 in addition to those taken at baseline and days 90 and 180. These photos will be used to test inter and intra rater reliability among two unblinded clinicians and three blinded clinicians. For more details, see section 10.2.1.

# 7 GENERAL ISSUES FOR STATISTICAL ANALYSIS

## 7.1 ANALYSIS SOFTWARE

Analysis data sets, statistical analyses and associated output generated by Boston Biomedical Associates (BBA) will be programmed using SAS® Software version 9.4 or later or R version 3.2.3 or later. BBA Standard Operating Procedures (SOPs) will be followed in the creation and validation of all analysis datasets, tables, listings, figures and analyses.

## 7.2 DISPOSITION OF SUBJECTS AND WITHDRAWALS

All subjects who provide written informed consent will be accounted for, and for purposes of subject accountability completeness, screen failures will also be presented. The frequency and percent of subjects in each analysis population (percentages will be based on number of enrolled subjects). The number and percent of ITT subjects who completed each scheduled assessment will be presented in a table. The number and percent of ITT subjects who prematurely withdrew from the study will be presented overall and by reason for discontinuation (subject withdrew consent, subject terminated prematurely by sponsor, subject non-compliance, adverse event/serious adverse event, other).

A flow chart and listing will also summarize subject accountability.

## 7.3 METHODS FOR WITHDRAWALS, MISSING DATA, AND OUTLIERS

All reasonable efforts will be made to obtain complete data for all subjects; however, missing observations most likely will occur. For the primary analysis on the primary efficacy endpoint, missing data will be imputed as a non-responder (i.e., imputed as “less than 20 mm^2 lift”). In the case that a subject has a Day 60 image evaluation but is missing the Day 90 image evaluation, the Day 60 evaluation will be carried forward in the primary endpoint analysis. As a sensitivity analysis, the primary analysis on the primary efficacy endpoint will also be carried out only on subjects with available data. For all remaining efficacy endpoints and for safety endpoints, there will be no imputation of missing data prior to analysis.

Tables detailing missing data and analysis populations will be provided in the final report.

## 7.4 PROTOCOL VIOLATIONS

Protocol violations will be summarized in the CSR. This summary will include the number and percent of subjects (overall and by site) with each violation type. Major protocol violations that may exclude a subject from the PP analysis population are identified in a study evaluability checklist and are included in Attachment 1.

## 7.5 MULTIPLE COMPARISONS AND MULTIPLICITY

No adjustments for multiple comparison will be made, as secondary endpoints will not undergo formal statistical testing in support of labeling claims.

## 7.6 ASSESSMENT OF HOMOGENEITY

As this is a single-site study, no analysis will be performed for site homogeneity. Assessment of homogeneity across sex, age groups, and condition types will be performed as outlined in Section 12.

# 8 DEMOGRAPHICS AND OTHER BASELINE CHARACTERISTICS

## 8.1 DEMOGRAPHICS

Age at screening (in years), sex (Male, Female), race (Not Done, White, Black or African American, American Indian/Alaskan Native, Asian, Native Hawaiian or Other Pacific Islander, Unknown, Other), ethnicity, height (inches), weight (lbs), BMI, heart rate (bpm), as well as systolic and diastolic blood pressure (mmHg) for all ITT subjects will be summarized in a table. For continuous variables, the summary will include sample size, mean, median, standard deviation, minimum and maximum. For categorical variables, the summary will include number and percent of ITT subjects.

## 8.2 PRIOR AND CONCURRENT MEDICATIONS

A listing will be provided detailing subjects' medications, but no table is planned at this time.

## 8.3 BASELINE MEDICAL HISTORY

The medical history of all ITT subjects will be summarized in a table. For each condition, the number and percent of subjects who do not have any history of the condition, who currently have the condition, and who have a resolved history of the condition will be presented.

## 8.4 SCREENING PHYSICAL EXAM

All subjects will undergo a physical examination for examination of various body systems. For each body system, the number and percentage of ITT subjects considered normal and abnormal will be presented.

# 9 TREATMENT DETAILS

For the ITT population, descriptive statistics of number of incisions made, number of RF passes, maximum temperature reached, average temperature reached, surface temperature, and time per unit area will be presented. Descriptive statistics consist of sample size, mean, median, standard deviation, minimum and maximum. These will be presented for right-lateral, frontal, left-lateral, and total.

## 10 EFFECTIVENESS ANALYSES

The following analyses will be carried out on the ITT and PP populations.

### 10.1 PRIMARY EFFECTIVENESS VARIABLE

The primary endpoint is an evaluation of the proportion of subjects with greater than 20 mm^2 lift at Day 90. The following hypothesis will be tested:

$$\begin{aligned} H_0: \pi &\leq 0.45 \text{ (or 45\%)} \\ H_a: \pi &> 0.45 \text{ (or 45\%)} \end{aligned}$$

where  $\pi$  is the proportion of subjects with greater than 20 mm^2 lift at Day 90. Statistical summaries will include the number and percentage of subjects with greater than 20 mm^2 lift at Day 90 and a two-sided 90% confidence interval of the percentage based on the exact binomial distribution. A one-sided exact binomial proportion test will be performed at  $\alpha=0.05$ . For the ITT population, the analysis will be carried out twice as follows:

1. Any subject with missing data at Day 60 and Day 90 will be treated as non-response to the photography (primary analysis). In the case that a subject has a Day 60 image evaluation but is missing the Day 90 image evaluation, the Day 60 evaluation will be carried forward in the primary endpoint analysis.
2. Any subject with missing data at Day 60 and Day 90 will be removed. In the case that a subject has a Day 60 image evaluation but is missing the Day 90 image evaluation, the Day 60 evaluation will be carried forward in the primary endpoint analysis.

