7.8. Prior and Concomitant Medications and Therapies

7.8.1 Permitted

Subjects will be allowed to continue with their usual necessary medical therapies, with no medically unnecessary changes in their diet or overall lifestyle. If medical conditions exist at the start of the study that require drug therapy during the study, those conditions and any concomitant medications prescribed should be recorded in the subject's source documents and the appropriate section of the CRF.

Subjects must abstain from exclusionary procedures/medications/therapies as listed under the Exclusion Criteria for the duration of the study.

Investigational Device: ThermiRF

Protocol No.: Thermi_0005

Version Date: Final 10-May-2016

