11.1. Study Hypothesis

The aim of this study is to evaluate the safety and effectiveness of the ThermiRF™ in the treatment of submental skin laxity with respect to “Lift”. The study design assumes that at least 70% of the population that consists of the target demographic (those that meet the inclusion/exclusion criteria) will have 20 mm² or more of lift. The null hypothesis is that subjects have a response rate of 45% or lower.

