11.2. Sample Size Determination

The sample size calculation is based on the following assumptions:

- The true response rate for subjects that do not drop out will be 70%.
- The null response rate is 45%, so a successful trial will reject the null hypothesis that the true response rate is less than or equal to 45%.
- The dropout rate will be approximately 12.5%. While some subjects that drop out may have data from Day 60 that can be carried forward in the primary effectiveness analysis, the sample size calculation assumes that none does and will therefore be treated as non-responders.
- The primary effectiveness analysis is based on a one-sided binomial proportion test that compares the null proportion to the alternative proportion.

Based on these assumptions, a minimum of 68 subjects is required to achieve 80% power at one-sided $\alpha = 0.05$, so a sample size of 70 subjects provides greater than 80% power.

Additionally based on the rule of three, sample size of at least 60 makes it possible to observe any adverse event that occurs with a frequency $> 5\%$ with 95% confidence.

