11.5. Analyses

11.5.1 Primary Effectiveness Analysis

The primary effectiveness analysis will compare the proportion of subjects who respond to treatment by achieving at least 20 mm² of lift of the submental region to a null proportion 45% using a one-sided binomial proportion test at $\alpha = 0.05$. Responders will be determined based on change from baseline of area as measured by Vectra XT 3D photography in standard lighting conditions. The primary effectiveness analysis will be based on the ITT population, so any missing data, including withdrawn consent and lost to follow up, will be treated as non-response.

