Study Specific Details and Rationale: All protocol specified withdrawal criteria should be reviewed to determine the status of "important" and if documentation exists supporting the non-withdrawal of the subject as well as discussions between the investigator and the sponsor.				
EXCLUDED MEDICATION OR DEVICE		Yes		

DEVIATION CATEGORY	DEVIATION SUBCATEGORY	Selected for study? Yes/No	MEETS THE DEFINITION OF MAJOR?	EXCLUDED FROM PER PROTOCOL ANALYSIS?
Role Responsible for Identification and Tracking:  Sponsor Clinical	a. Medication or dose of medication, excluded by the protocol, was administered	Yes	Y	N
	b. Device, excluded by the protocol, was administered (Example: received another device treatment during study conduct)	Yes	Y	Y

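### A Day 90 image taken after a prohibited procedure is scored as observed in the primary ITT analysis, so lift from another treatment can count as a ThermiRF response

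*SAP*

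**What the plan says.** **The ban.** Protocol 6.3.2 lists the exclusionary cosmetic treatments, among them skin tightening, fillers, lasers, neck lift and threads. Protocol 7.8.1 carries the list forward: "Subjects must abstain from exclusionary procedures/medications/therapies as listed under the Exclusion Criteria for the duration of the study".

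**What happens after a breach.** Under Protocol 8.6, withdrawal is at the discretion of the investigator or sponsor. A subject who has a prohibited procedure can therefore stay and have a Day 90 image taken.

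**Primary scoring.** The population is all enrolled eligible subjects (Protocol 11.3, SAP 6.1). Apart from an observed lift below the threshold, non-response is assigned only for missing data:
- Protocol 11.5.1: "any missing data, including withdrawn consent and lost to follow up, will be treated as non-response".
- SAP 10.1: "Any subject with missing data at Day 60 and Day 90 will be treated as non-response to the photography (primary analysis"). SAP 7.3 agrees, and both carry a Day 60 image forward when the Day 90 image is missing.

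**Where a breach does count.** The evaluability checklist in SAP Appendix 1 foresees a subject who "received another device treatment during study conduct". It rates this as major and removes the subject from the per-protocol (PP) population. For an excluded medication, the same checklist says major but not removed from PP. Protocol 11.3 and SAP 6.2 both define PP as free of excluded-medication use.

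**The concern.** The sponsor anticipated that a subject might receive another treatment during follow-up and gave that event a consequence in PP, but none in the confirmatory analysis. Several of the banned procedures could plausibly alter the submental area that the 3D system measures. An image taken after one of them reflects ThermiRF plus the other treatment, and the primary rule credits all of it to ThermiRF.

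In a randomised trial a control arm would share such contamination to some degree. Here each subject is compared with his or her own baseline and the proportion is tested against a constant, so nothing offsets it. The direction is towards success, in the one analysis the trial is powered for. The plan is already conservative about missing images, so silence on a known competing treatment is out of step with its own approach.

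**Working it through.** **Inputs**
- Null rate 45% (Protocol 11.1: "The null hypothesis is that subjects have a response rate of 45% or lower").
- Response of 70% in subjects who stay (Protocol 11.2: "The true response rate for subjects that do not drop out will be 70" percent).
- Dropout (SAP 5): "The dropout rate is 12.5% and all dropouts will be considered as non-responders".
- n = 70; one-sided exact binomial test at 0.05 (SAP 5 and 10.1).
- k, the number of subjects with a prohibited procedure before the image: **not in the documents**. The range k = 1 to 3 is assumed for illustration.

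**Step 1: reproduce the plan's power.** The ITT response rate is 0.70 × 0.875 = 0.6125. The smallest r with P(Bin(70, 0.45) ≥ r) ≤ 0.05 is r = 39 (55.7%), with attained size 0.0467. Power is P(Bin(70, 0.6125) ≥ 39) = 0.858. The SAP's approximate 85% reproduces.

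**Step 2: sensitivity of the decision to one subject.** 38/70 gives p = 0.075 and 39/70 gives p = 0.047. One reclassified subject can decide the result.

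**Step 3: false success under the current rule, true rate 45%.** Two definitions of k are possible.
- (a) k subjects have a procedure and all score as responders. The other 70 − k must supply 39 − k: P(Bin(70 − k, 0.45) ≥ 39 − k).
- (b) k counts only subjects who would not have responded and are converted by the procedure: P(Bin(70, 0.45 + k/70) ≥ 39).

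**Step 4: effect of counting the k subjects as non-responders.** The other 70 − k must supply all 39.
- Power: P(Bin(70 − k, 0.6125) ≥ 39).
- False success: P(Bin(70 − k, 0.45) ≥ 39).

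| k | False success now, (a) | False success now, (b) | False success with fix | Power with fix |
|---|---|---|---|---|
| 0 | 4.7% | 4.7% | 4.7% | 85.8% |
| 1 | 6.0% | 7.5% | 3.6% | 82.4% |
| 2 | 7.6% | 11.6% | 2.7% | 78.4% |
| 3 | 9.5% | 16.9% | 2.0% | 73.9% |

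Columns (a) and (b) differ only in what k counts. At a 45% rate, a fraction 0.55 of subjects with a procedure would otherwise have failed, so one converted non-responder corresponds to about 1/0.55 = 1.8 subjects with a procedure. That is why (b) at k = 1 is close to (a) at k = 2. Definition (a) matches a count of subjects with a recorded procedure and is used as the main figure.

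**Step 5: do the other planned analyses catch it?**
- The second ITT analysis in SAP 10.1 changes only how missing images are treated, so it does not address the issue.
- The PP analysis (Table 9.1) removes excluded-device subjects. For an injectable recorded as a medication, the result depends on whether the PP definitions or the checklist is followed, and these conflict.

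**The case against.** The best defence is that analysing observed values in ITT regardless of deviations is a recognised strategy, and that the plan has a second look. The primary endpoint is tested again in PP with its own p-value, and excluded-device subjects are out of that population. Contamination by devices would then tend to appear as disagreement between ITT and PP. That is a fair point and limits the concern. It does not remove it: PP is supportive and cannot change the primary result, the documents disagree about excluded medication, and without a control arm the observed-value strategy credits the other treatment to the device.

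Four stronger readings are tempting and are not supported.
- *A subject who switches and leaves always fails, while one who stays can succeed.* This holds only without a Day 60 image. The first 30 subjects have Day 60 3D photography (Protocol 6.1 and 8.4), and SAP 7.3 and 10.1 carry that result forward, so a leaver among them can still be a responder.
- *The secondary endpoints have the same fault.* Their images and scores are also taken as observed. However, SAP 10.2 drops missing secondary data instead of failing them, and SAP 7.5 says these endpoints are not formally tested in support of labelling claims. The consequence is much smaller.
- *False success of 7.5% to 16.9% is the expected size.* Those figures apply only if k counts converted non-responders. Even the lower set is a worst case, because every procedure is assumed to end in a scored response.
- *Any lower-face treatment should mean failure.* That would fail genuine responders for treatments that cannot affect the submental area.

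**Conclusion.** The gap is real and narrow. No text in either document says how an image taken after a prohibited procedure counts in the primary analysis, so by default it counts as seen, and any resulting bias favours ThermiRF. Its size cannot be estimated from the documents, because no rate of such procedures is given. Under the assumed 1 to 3 subjects of 70, all scoring as responders, false success is 6.0% to 9.5% against an attained 4.7%, and it already exceeds the nominal 5% at one subject. If no such procedures occur, the result is unaffected.

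A reader might infer that the primary test is invalid as planned, or that PP offers no protection. Neither follows: the test holds its size at k = 0, and PP removes the excluded-device cases. The point should be settled in the SAP before Day 90 results are seen, because after that the choice of rule could decide a result close to 39 of 70.

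**What to change.** In SAP 7.3 and 10.1, add a scoring rule to the primary analysis along these lines:

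> *A subject who, after Visit 2 and before the image used for the endpoint, receives a protocol-prohibited procedure, injectable or device treatment that could change the submental area is counted as a non-responder, whatever the measured lift. A Day 60 image taken before the procedure may be carried forward only under the existing rule for a missing Day 90 image.*

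Then:
- list in advance which prohibited treatments are taken to affect the submental area;
- show the number of subjects affected in Table 7.1, with the result using observed values as a sensitivity line;
- reconcile Protocol 11.3 and SAP 6.2 with the SAP Appendix 1 checklist on excluded medication in PP.

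Extending the rule to the dichotomised secondary endpoints is optional. The change concerns scoring only, not how subjects are managed.

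**Cost.** SAP wording and one derivation. Each affected subject who would have scored as a responder lowers the observed rate by 1/70, or 1.4 percentage points. Power falls from 85.8% to 82.4%, 78.4% and 73.9% for one, two and three affected subjects, which is below the protocol's 80% target from two onwards. Identification would rest on deviation tracking (Protocol 8.6.1) and concomitant-medication records. The schedule in Protocol Appendix 1 has no item asking about aesthetic procedures, so the sponsor should confirm that the case report forms capture them with dates. If the sponsor prefers to keep observed values as primary, the minimum is to say so explicitly and prespecify the non-responder version as a sensitivity analysis.
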